## 5.4.1 Emergency Medical Contacts

To ensure the safety of study patients, an Emergency Medical Call Center Help Desk will access the Roche Medical Emergency List, escalate emergency medical calls, provide medical translation service (if necessary), connect the investigator with a Roche Medical Responsible (listed above and/or on the Roche Medical Emergency List), and track all calls. The Emergency Medical Call Center Help Desk will be available 24 hours per day, 7 days per week. Toll-free numbers for the Help Desk, as well as Medical Monitor and Medical Responsible contact information, will be distributed to all investigators.

## 5.4.2 Reporting Requirements for Serious Adverse Events and Adverse Events of Special Interest

## 5.4.2.1 Events That Occur Prior to Study Drug Initiation

After informed consent has been obtained but prior to initiation of study drug, only serious adverse events caused by a protocol-mandated intervention should be reported. The paper Clinical Trial Serious Adverse Event/Adverse Event of Special Interest Reporting Form provided to investigators should be completed and submitted to the Sponsor or its designee immediately (i.e., no more than 24 hours after learning of the event), either by faxing or by scanning and emailing the form using the fax number or email address provided to investigators.

## 5.4.2.2 Events That Occur After Study Drug Initiation

After initiation of study drug, serious adverse events and adverse events of special interest will be reported until the final study visit. For patients who terminate from study treatment and study early, all adverse events will be collected up to the early termination visit. Investigators should record all case details that can be gathered immediately (i.e., within 24 hours after learning of the event) on the Adverse Event eCRF and submit the report via the electronic data capture (EDC) system. A report will be generated and sent to Roche Safety Risk Management by the EDC system.

In the event that the EDC system is unavailable, the paper Clinical Trial Serious Adverse Event/Adverse Event of Special Interest Reporting Form provided to investigators should be completed and submitted to the Sponsor or its designee immediately (i.e., no more than 24 hours after learning of the event), either by faxing or by scanning and emailing the form using the fax number or email address provided to investigators. Once the EDC system is available, all information will need to be entered and submitted via the EDC system.

Instructions for reporting post-study serious adverse events are provided in Section 5.6.

## 5.4.3 Reporting Requirements for Pregnancies

## 5.4.3.1 Pregnancies in Female Patients

Female patients of childbearing potential will be instructed through the Informed *Consent Form* to immediately inform the investigator if they become pregnant during the study or within 28 days after the last intravitreal ranibizumab injection or 1 year after the last implant ranibizumab refill-exchange. A paper Clinical Trial Pregnancy Reporting Form should be completed and submitted to the Sponsor or its designee immediately (i.e., no more than 24 hours after learning of the pregnancy), either by faxing or by scanning and emailing the form using the fax number or email address provided to investigators. Pregnancy should not be recorded on the Adverse Event eCRF. The investigator should discontinue study drug and counsel the patient, discussing the risks of the pregnancy and the possible effects on the fetus. If medically necessary, as per investigator's judgment and after discussion with the Medical Monitor, a saline flush of implant content may be performed for patients in the implant arm. Monitoring of the patient should continue until conclusion of the pregnancy. Any serious adverse events associated with the pregnancy (e.g., an event in the fetus, an event in the mother during or after the pregnancy, or a congenital anomaly/birth defect in the child) should be reported on the Adverse Event eCRF. In addition, the investigator will submit a Clinical Trial Pregnancy Reporting Form when updated information on the course and outcome of the pregnancy becomes available.

## 5.4.3.2 Abortions

A spontaneous abortion should be classified as a serious adverse event (as the Sponsor considers abortions to be medically significant), recorded on the Adverse Event eCRF, and reported to the Sponsor immediately (i.e., no more than 24 hours after learning of the event; see Section 5.4.2).

If a therapeutic or elective abortion was performed because of an underlying maternal or embryofetal toxicity, the toxicity should be classified as a serious adverse event, recorded on the Adverse Event eCRF, and reported to the Sponsor immediately (i.e., no more than 24 hours after learning of the event; see Section 5.4.2). A therapeutic or elective abortion performed for reasons other than an underlying maternal or embryofetal toxicity is not considered an adverse event.

All abortions should be reported as pregnancy outcomes on the paper Clinical Trial Pregnancy Reporting Form.

# 5.4.3.3 Congenital Anomalies/Birth Defects

Any congenital anomaly/birth defect in a child born to a female patient exposed to study drug should be classified as a serious adverse event, recorded on the Adverse Event eCRF, and reported to the Sponsor immediately (i.e., no more than 24 hours after learning of the event; see Section 5.4.2).

# 5.4.4 Reporting Requirements for Medical Device Complaints

The investigator must report all complaints associated with medical device and their packaging to the Sponsor no more than 24 hours after learning of the event.

In this study, the PDS implant, the PDS ancillary devices, and the intravitreal ranibizumab 0.5 mg single-use container are considered medical devices.

To report a medical device complaint, the investigator should follow the guidance outlined in the Device Complaints and Return Instructions for the Clinical Sites document and provide as much information as possible to the Sponsor, including the product batch number.

If the medical device results in an adverse event to the study patient, the event must be reported on the Adverse Event eCRF and submitted through the EDC system by the investigator. If the event is serious, the Adverse Event eCRF must be completed immediately (i.e., no more than 24 hours after learning of the event), as outlined in Section 5.4.2. If a medical device causes an adverse event to an individual other than the study patient (e.g., study site personnel), the event should be reported to the Sponsor (refer to the Device Complaints and Return Instructions for the Clinical Sites for further details).

For further information on returning the PDS implant and the ancillary devices associated with a complaint, refer to the Device Complaints and Return Instructions for the Clinical Sites document.

#### 5.4.4.1 Device Defects or Deficiencies That Could Have Led to Medical Occurrence

Device deficiencies (inadequacy with respect to labeling, identity, quality, durability, reliability, safety, or performance, including malfunctions) that did not lead to an adverse event but could have led to a medical occurrence if suitable action had not been taken, must be reported immediately (i.e., no more than 24 hours after learning of the event). Refer to the Device Complaints and Return Instructions for the Clinical Sites for further details.

# 5.5 FOLLOW-UP OF PATIENTS AFTER ADVERSE EVENTS

## 5.5.1 Investigator Follow-Up

The investigator should follow each adverse event until the event has resolved to baseline grade or better, the event is assessed as stable by the investigator, the patient is lost to follow-up, or the patient withdraws consent. Every effort should be made to follow all serious adverse events considered to be related to study drug or trial-related procedures until a final outcome can be reported.

During the study period, resolution of adverse events (with dates) should be documented on the Adverse Event eCRF and in the patient's medical record to facilitate source data verification.

All pregnancies reported during the study should be followed until pregnancy outcome.

## 5.5.2 Sponsor Follow-Up

For serious adverse events, adverse events of special interest, and pregnancies, the Sponsor or a designee may follow up by telephone, fax, email, and/or a monitoring visit to obtain additional case details and outcome information (e.g., from hospital discharge summaries, consultant reports, autopsy reports) in order to perform an independent medical assessment of the reported case.

#### 5.6 ADVERSE EVENTS THAT OCCUR AFTER THE ADVERSE EVENT REPORTING PERIOD

The Sponsor should be notified if the investigator becomes aware of any serious adverse event that occurs after the end of the adverse event reporting period (defined as 30 [+7] days after the last dose of study drug for intravitreal arm; the final study visit for patients in the implant arm; and 90 [+7] days after explantation for patients who undergo implant explantation), if the event is believed to be related to prior study drug treatment. These events should be reported through use of the Adverse Event eCRF. However, if the EDC system is not available, the investigator should report these events directly to the Sponsor or its designee, either by faxing or by scanning and emailing the paper Clinical Trial Serious Adverse Event/Adverse Event of Special Interest Reporting Form using the fax number or email address provided to investigators.

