#### 4.6 TREATMENT, PATIENT, STUDY, AND SITE DISCONTINUATION

#### 4.6.1 Study Treatment Discontinuation

Patients must permanently discontinue study treatment if they experience any of the following:

- Any medical condition that the investigator or Sponsor determines may jeopardize the patient's safety if he or she continues to receive study treatment
- Investigator or Sponsor determination that treatment discontinuation is in the best interest of the patient
- Pregnancy
- Any treatment for nAMD not specified in the protocol

The primary reason for study treatment discontinuation should be documented on the appropriate eCRF. Patients who discontinue study treatment prematurely will not be replaced.

Upon study treatment discontinuation, patients in the implant arm will no longer receive implant refill-exchanges and patients in the intravitreal arm will no longer receive ranibizumab injections.

All patients who discontinue study treatment will be strongly encouraged to attend as many scheduled study visits as possible, with an emphasis on visits at Weeks 36, 40, and 96 (see Appendix 4 for the minimum required assessments to be performed). Per investigator judgment, patients may start an FDA-approved intravitreal anti-VEGF treatment for nAMD in the study eye after the decision to discontinue study treatment is made. Study-sponsored intravitreal ranibizumab 0.5 mg treatment will be provided for patients who discontinue from the implant arm only, if the anti-VEGF treatment chosen by the investigator is ranibizumab and until the patient completes the study.

The investigator must notify the Medical Monitor if the decision to perform explantation is made after study treatment discontinuation. Explanted patients will return for safety assessments at 1, 7 ( $\pm$ 2), 30 ( $\pm$ 7), and 60 ( $\pm$ 7) days post-explantation (see Appendix 4). All patients will be strongly encouraged to remain in the study after their last post-explantation safety visit. They can return for as many scheduled study visits as possible (with an emphasis on completing the Week 36, Week 40, and Week 96 visits). Patients may start an FDA-approved intravitreal anti-VEGF treatment in the study eye, including Sponsor-provided intravitreal ranibizumab 0.5 mg if chosen by the investigator once the need for explantation is confirmed and preferably after explantation is completed.

**Port Delivery System with Ranibizumab—F. Hoffmann-La Roche Ltd.** 70/Protocol GR40548, Version 5

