# 5.3.1 Adverse Event Reporting Period

Investigators will seek information on adverse events at each patient contact. All adverse events, whether reported by the patient or noted by study personnel, will be recorded in the patient's medical record and on the Adverse Event eCRF.

After informed consent has been obtained but prior to initiation of study treatment (Day 1), only serious adverse events caused by a protocol-mandated intervention (e.g., discontinuation of medications or intravitreal ranibizumab administered at screening or during run-in period) should be reported (see Section 5.4.2 for instructions for reporting serious adverse events).

After initiation of study treatment, all adverse events, regardless of relationship to study drug, implant, or ancillary devices, or study procedures, will be reported until the patient's final study visit. For patients who terminate study treatment and discontinue from the study prematurely, all adverse events will be reported up to the early termination visit. For patients who discontinue study treatment early but continue to participate in the study, adverse events will be reported until their last or final study visit.

Instructions for reporting adverse events that occur after the adverse event reporting period are provided in Section 5.6.

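### Protocol 5.6 ends the adverse event reporting period at a different point from 5.3.1 for patients who are off treatment or explanted but still on study; reconcile the two sections.

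*Protocol*

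**What the plan says.** Protocol 5.6 deals with events after the adverse event reporting period and, in a parenthesis, defines when that period ends. It gives three end points. The first two, one for each arm, are "30 [+7] days after the last dose of study drug for intravitreal arm; the final study visit for patients in the implant arm". The third applies to implant patients whose device is removed, and is set at "90 [+7] days after explantation for patients who undergo implant explantation". Beyond that point the sponsor is to be notified only of a serious event, and only "if the event is believed to be related to prior study drug treatment".

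Protocol 5.3.1, the section named for the reporting period, has one rule for both arms. After treatment starts, all adverse events "will be reported until the patient's final study visit". For patients who leave the study early, "all adverse events will be reported up to the early termination visit". For patients who stop treatment but stay, "adverse events will be reported until their last or final study visit".

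Such patients are foreseen. Protocol 4.6.1 says that those who stop study treatment "will be strongly encouraged to attend as many scheduled study visits as possible", with emphasis on Weeks 36, 40 and 96, and it encourages explanted patients to remain as well.

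**The concern.** One term has two definitions, and 5.3.1 itself sends the reader to 5.6 for later events, so a site meets both. Under 5.3.1, an intravitreal patient who stops injections at Week 24 and keeps attending has every adverse event reported to the last visit. Under 5.6, the same patient's period closes about a month after the last injection. From then on a non-serious ocular event of special interest, or a serious event judged unrelated, falls outside the notification rule in 5.6. An implant patient who stops refills without explantation is covered to the final visit under either section; an explanted patient is not.

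The safety objective compares the arms, including on adverse events of special interest, and the SAP counts events through study completion. An event left unreported because a site relied on 5.6 would enter that comparison as no event.

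**Working it through.** No sample size, power or alpha figure is involved, and the plan states no figure to reproduce. The check is day arithmetic followed by a comparison of sections.

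**Inputs**
- Last planned intravitreal dose at Week 92 (Protocol 4.3.2.2); nominal final visit at Week 96, which is 96 × 7 = Day 672.
- Visit windows of ±7 days (Appendix 2).
- 5.6 end points: last dose + 30 to 37 days; explantation + 90 to 97 days.
- Intravitreal early termination visit: last injection + 30 to 37 days (4.6.2).

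**Formula.** Shortfall = 672 − (7 × week of last dose + 30 to 37), or 672 − (7 × week of explantation + 90 to 97). A negative value means that the 5.6 period ends after Week 96.

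**Where the rules agree**
- Intravitreal completer: 7 × 92 = 644; 644 + 30 = 674 and 644 + 37 = 681. The 5.6 period ends 2 to 9 days after Week 96. With both visit windows the gap between last dose and final visit is 14 to 42 days, so 5.6 ends between 12 days before (30 − 42) and 23 days after (37 − 14) the final visit.
- Intravitreal patient who leaves the study: the early termination visit and the 5.6 end have the same 30-to-37-day window, so there is no difference.

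**Where they part: intravitreal patient followed to Week 96**

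| Last dose | Shortfall (days) | Weeks |
|---|---|---|
| Week 12 | 551–558 | about 79 |
| Week 24 | 467–474 | about 67 |
| Week 48 | 299–306 | about 43 |
| Week 72 | 131–138 | about 19 |
| Week 88 | 19–26 | about 3 |

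The Week 88 row is a patient who misses only the Week 92 injection, since missed injections are not made up (4.3.2.2).

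**Explanted patient followed to Week 96**

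| Explantation | Shortfall (days) |
|---|---|
| Week 24 | 407–414 |
| Week 48 | 239–246 |
| Week 72 | 71–78 |

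Break-even: 96 − 90/7 = 83.1. After explantation later than about Week 83, the 5.6 period runs past Week 96.

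**Which section is the outlier**
- 5.1.1 has all adverse events recorded throughout the study.
- 5.3.5.7 (deaths) cites 5.3.1, not 5.6, as the source of the reporting period.
- 5.4.2.2 has serious events and events of special interest reported to the final visit, with no distinction by arm.
- The schedules of activities for both arms (Appendices 1 and 2) record adverse events from Day 1 to the last visit.
- Appendix 4 lists adverse events among the assessments at visits after treatment discontinuation and after explantation.
- SAP 4.7.1 uses one treatment-emergent window for both arms, and SAP 4.7 bases the final summaries on cumulative Week 96 data. Neither has a 30-day cut.

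On this point 5.6 stands alone.

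**The case against.** The best defence is that 5.6 was never meant to govern collection. It tells sites what to do with related serious events that come to light later. The patients in question are covered by an express rule in 5.3.1, and every collection instruction listed above agrees with it. The 30- and 90-day figures resemble the early termination timings in 4.6.2 for patients who leave the study, so the likely defect is an unstated qualifier. The source of the figures is an inference, but the rest of this stands. A site would have to set aside several sections to lose the events.

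It does not clear 5.6, whose parenthesis is worded as a definition and is not limited to patients who have left. That the other sections are consistent shows which text to correct.

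A reader might go further and infer that safety ascertainment is unequal between the arms and that the Week 96 comparison is biased. The documents do not support that. They direct collection to the last visit in both arms, and the SAP analyses both arms over the same window. The explantation clause would also truncate some implant patients, so even under a literal use of 5.6 the net direction is unknown. The week counts above measure time outside the period as 5.6 defines it; they do not count uncollected events. Nor does anything show that unequal collection was chosen.

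**Conclusion.** The inconsistency is real and of low severity. 5.6 and 5.3.1 give different ends to the same period. The difference is immaterial for intravitreal completers dosed at Week 92 and for patients who leave the study. For intravitreal patients off treatment but on study it runs from about 3 weeks (last dose Week 88) to about 79 weeks (last dose Week 12); for patients explanted at Week 72 to Week 24 who stay, it is about 10 to 59 weeks (71/7 to 414/7).

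These figures assume nominal visit dates and follow-up to Week 96. Any loss of safety data depends on a site having applied 5.6 as its cut-off, which the documents do not show. They also give no count of patients off treatment or explanted but still on study, so the size of the risk cannot be computed.

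**What to change.** Rewrite the parenthesis in 5.6 to match 5.3.1: the period ends at the final study visit, or at the early termination visit for patients who leave, in both arms, including patients off treatment or explanted who remain on study. Keep the existing 90 [+7]-day post-explantation window wherever it ends later than the final visit. Without that clause, the rewrite would shorten reporting for patients explanted after about Week 83.

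The cost is one sentence, with no new visits or assessments, because Appendix 4 already schedules adverse event assessment at the visits that these patients attend. As SAP Version 3 was prepared for the final report, it would also be sensible to check from a listing that adverse events in these patients were captured to their last visit.

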#### 5.7 EXPEDITED REPORTING TO HEALTH AUTHORITIES, INVESTIGATORS, INSTITUTIONAL REVIEW BOARDS, AND ETHICS COMMITTEES

The Sponsor will promptly evaluate all serious adverse events and adverse events of special interest against cumulative product experience to identify and expeditiously communicate possible new safety findings to investigators, IRBs, ECs, and applicable health authorities based on applicable legislation.

To determine reporting requirements for single adverse event cases, the Sponsor will assess the expectedness of these events using the following reference document:

• PDS Investigator's Brochure

The Sponsor will compare the severity of each event and the cumulative event frequency reported for the study with the severity and frequency reported in the applicable reference document.

Reporting requirements will also be based on the investigator's assessment of causality and seriousness, with allowance for upgrading by the Sponsor as needed.

#### 6. STATISTICAL CONSIDERATIONS AND ANALYSIS PLAN

The primary analysis will be performed when all patients have completed the Week 40 visit or have discontinued from the study prior to Week 40, all data collected through Week 40 are in the database, and the data have been cleaned and verified. At the time of the primary analysis, the study will be ongoing. An analysis of the available data post Week 40 (after Week 40 and up to a specified clinical cutoff date) will also be performed. Such results will be reported with, but separate from, the 40-week study results to provide additional information.

Additional analyses may be performed to support the requirements of health authorities relative to marketing applications, as appropriate.

The final analysis will be performed after all patients have either completed the 2-year study treatment period including their final study visit, or discontinued early from the study, all data from the study are in the database, and the database is locked.

The primary analysis, summarized by treatment group, may be reported to the public before completion of the study.

Descriptive summaries will include the mean, standard deviation, median, and range for continuous variables, and counts and percentages for categorical variables.

Detailed specifications of the statistical methods will be described in the Statistical Analysis Plan (SAP).

#### 6.1 DETERMINATION OF SAMPLE SIZE

Patients will be randomly allocated in a 3:2 ratio to the implant arm or intravitreal arm.

The primary endpoint is the change in BCVA score from baseline averaged over Weeks 36 and 40. The study is sized to achieve adequate power to show non-inferiority (NI) and equivalence of the implant arm to the intravitreal arm in the change in BCVA score from baseline averaged over Week 36 and Week 40 using an NI margin of 4.5 letters and equivalence margins of  $\pm$ 4.5 letters.

**Port Delivery System with Ranibizumab—F. Hoffmann-La Roche Ltd.** 103/Protocol GR40548, Version 5

Assuming a standard deviation of 9.5 letters for the change from baseline in BCVA score averaged over 36 and 40 weeks, up to a true mean change from baseline in BCVA of 0.75 letters worse for the implant arm, compared with the monthly intravitreal arm, 216 patients in the implant arm and 144 patients in the intravitreal arm will provide >90% power to demonstrate NI and equivalence between the two treatment groups. Calculations were based on a one-sided t-test at  $\alpha = 0.025$  level for the NI test and two one-sided t-tests at the  $\alpha = 0.025$  level for the equivalence test with the assumption of a 10% dropout rate by Week 40 and a 10% increase for the trimmed mean analysis.

An independent statistician was employed to conduct a masked evaluation of the variance of the primary efficacy endpoint, but not the proportion of patients who receive supplemental treatment during the study or the study dropout rate before the end of enrollment because the enrollment was too rapid for these evaluations to be of value. The variance comparison to the assumptions used in planning the study did not suggest the initial assumption for the variance of the primary efficacy endpoint was substantially lower. However, independent of this assessment, due to a high speed of enrollment combined with a lower screen failure rate than expected, the number of patients enrolled was unintentionally increased to 418. Details of the masked assessment, findings, and actions will be documented in the SAP.

